8.5 Missing Data

Under the ITT principle, all patients who are randomized are included in the analysis. Therefore, missing data, especially in the primary outcome measure, can be problematic. For the primary futility analysis we will impute missing data using multiple imputation [Rubin, 1987] assuming a monotone missing mechanism and missing is at random (MAR). Similar methods will be employed for secondary analyses and secondary outcomes. For safety data (AEs) no data imputation will be done.

8.6 Interim Analysis

No formal interim analyses are planned.

8.7 Adjusting for Covariates

The primary analysis will be adjusted for site and baseline stroke severity (AQ).

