2.2.2 Procedures for Diagnostic Testing (Visit 1)

If the patient passes the screening portion, diagnostic testing will be conducted during the same visit. The following diagnostic testing procedures will be performed:

1. Administer the *Western Aphasia Battery-Revised* (WAB-R):
 - o The WAB-R will characterize the patients' overall language impairment through the evaluation of the main clinical aspects of language functioning, including speech content, speech fluency, auditory comprehension, repetition, and naming. The WAB-R allows for the differentiation of these specific language abilities, as well as the classification of aphasia type. The WAB-R also yields a composite score, the Aphasia Quotient, which provides an overall measure of severity, in which lower scores denote more severe aphasia (Kertesz, 2007). Speech-language pathologists (SLPs) will refer to the manual for explicit instructions regarding administration and scoring procedures. Administration time will range between 30-45 minutes.
2. Administer the *Boston Naming Test-Second Edition* (BNT):
 - o The BNT represents a measure of object naming abilities from a corpus of 60 line drawings. Object names are ranked along a continuum, with easier, more higher-frequency words appearing at the beginning of the test and more difficult, lower-frequency words appearing near the end. To eliminate patient frustration, the BNT implements a ceiling effect so that once the patient incorrectly names eight items in a row, testing will cease, with the assumption that (s)he would not correctly name the upcoming, more difficult words (Kaplan, Goodglass, & Weintraub, 2001). SLPs will refer to the manual for explicit instructions regarding administration and scoring procedures. Administration time will range between 5-20 minutes.
3. Administer Subtest 6 from the *Apraxia Battery for Adults-Second Edition* (ABA-2):

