3.2 Randomization and Blinding

The study is to be conducted in a double-blind manner. The subjects, the site investigators, and the USC and MUSC clinical staff involved in this study will not know the treatment assignment. Select members of the Statistical and Data Management Center will be partially blinded, i.e., they will know the treatment group assignment as A or B, but not whether the patient receives active tDCS or sham. The study statistician and the DSMB will have a sealed envelope with the treatment group identifiers. This envelope would only be opened if the study statistician is directed to open it by the DSMB or at the end of the futility study.

The randomization will take place centrally via the Trial Website. Subjects will be randomized 1:1 (A-tDCS: S-tDCS), controlling for clinical center, aphasia type, and severity (classified using the Western Aphasia Battery revised: WAB-R). The computer program developed at the DCU makes the treatment assignment based on the current status of treatment group distribution within each stratum as well as overall balance of treatment assignment. The randomization scheme will never be deterministic. The detailed randomization scheme and source codes will be provided in the Randomization Plan document.

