A “Real-Time” randomization procedure is implemented via the Trial Website on the WebDCU™ System where the clinical center staff enters the basic baseline (e.g. aphasia type, and AQ severity) and eligibility information of a subject prior to enrollment. If the subject’s eligibility status is confirmed, the computer program on the WebDCU™ server will evaluate the treatment arm distribution and generate a patient number based on the randomization scheme. The SLP enrolling the patient will not see the treatment assignment, only a numeric patient number which is entered into a software package that controls whether the tDCS given is A-tDCS or S-tDCS. In order to mask treatment type (A-tDCS vs. S-tDCS) for both patients as well as the SLPs administering the treatment session (ie. setting up the tDCS and starting and monitoring the computerized treatment task), we use in-house software/hardware. As previously discussed, this setup allows for switching the tDCS on and off without any involvement from the patient or experimenter. The software is run on a lap-top computer connected to the tDCS stimulator. Treatment type is encoded in the software so that the administrator only needs to enter a patient and session number to start stimulation without knowing whether those specific numbers are

associated with A-tDCS or S-tDCS. The unblinded list of randomization codes and treatment assignments will be generated by the DCU and will be uploaded into the software by a software administrator who is not otherwise involved in the study.

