3.4.7 Adjusting for Covariates

The primary analysis will be adjusted for clinical site, aphasia type, and baseline aphasia severity (AQ).

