6. RANDOMIZATION AND BLINDING

The study is to be conducted in a double-blind manner. The subjects, the site investigators, and the USC and MUSC clinical staff involved in this study will not know the intervention assignment. Select members of the Data Coordination Unit (DCU) will be partially blinded, i.e., they will know the intervention group assignment as A or B, but not whether the patient receives active tDCS or sham. The study statistician and the DSMB will have a sealed envelope with the intervention group identifiers. This envelope would only be opened if the study statistician is directed to open it by the DSMB or at the end of the futility study.

The randomization will take place centrally via the trial Website (WebDCU). Subjects will be randomized 1:1 (A-tDCS: S-tDCS). The objective of subject randomization is to protect the randomness of treatment allocation and to prevent serious imbalances in site, baseline age, aphasia type, and severity (as measured by the WAB-R). The block urn method (Zhao et al. 2011) and the minimal sufficient balancing method (Zhao et al. 2012) will be used. The computer program developed at the DCU makes the treatment assignment based on the current status of treatment group distribution within each stratum as well as overall balance of treatment assignment. The randomization scheme will never be deterministic.

A “Real-Time” randomization procedure is implemented via the Trial Website on the WebDCU™ System where the clinical center staff enters the basic baseline (e.g., age, aphasia type, and AQ severity) and eligibility information of a subject prior to enrollment. If the subject’s eligibility status is confirmed, the computer program on the WebDCU™ server will evaluate the treatment arm distribution and generate a treatment assignment based on the randomization scheme. The clinician (speech-language pathologist – SLP) enrolling the patient will not see the treatment assignment, only a numeric patient number.

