9.2 Exploratory Analyses of the Primary Outcome measures

Spearman's correlation coefficients will be computed for pre-post change in anomia versus aphasia type first using all patients and then by tDCS group. This association will be further explored using the longitudinal data in a GLMM model described in section 3.14 (post-testing phase). Since there will be little statistical power to detect an interaction of aphasia type and treatment, we will examine the main effect of aphasia type (adjusting for the other covariates) by tDCS group.

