9.3 Post-Testing Phase

The longer follow-up post-testing phase will provide exploratory information on whether the immediate post-testing improvement after 3 weeks of treatment can be sustained. The mean (95% CI) changes from baseline to immediate (within 1 week) post-testing, 4 weeks post-testing and 6 months post-testing will be reported. Box and whisker plots will be produced to show the distribution of naming accuracy over time by group.

To explore the longitudinal data, a Repeated Measures model (SAS® MIXED procedure with REPEATED sub-command) will be constructed by tDCS group. The model will include the following fixed effects: visit (as a classification variable), aphasia type, severity, and clinical center as independent variables. Various error structures will be examined (e.g., compound symmetry, autoregressive, unstructured), and the final structure will be selected based on the model Akaike Information Criteria. A similar modeling approach may be applied to other secondary outcomes (e.g., number of naming errors).

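### The protocol and SAP give different covariate lists for the one primary futility test: the SAP drops aphasia type, and age is balanced in the SAP but adjusted for in neither document

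*SAP*

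**What the plan says.** On the primary model:

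- Protocol 3.4.7: "The primary analysis will be adjusted for clinical site, aphasia type, and baseline aphasia severity (AQ".
- SAP 8.7: "The primary analysis will be adjusted for site and baseline stroke severity (AQ".

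On allocation:

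- Protocol 3.2 randomises "controlling for clinical center, aphasia type, and severity". In its account of real-time randomisation, site staff "enters the basic baseline (e.g. aphasia type, and AQ severity) and eligibility information". Age is not mentioned.
- SAP 6 aims "to prevent serious imbalances in site, baseline age, aphasia type, and severity (as measured by the WAB-R", so age is a balancing factor there.

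Elsewhere the SAP keeps aphasia type. The longitudinal model in SAP 9.3 has fixed effects for "visit (as a classification variable), aphasia type, severity, and clinical center as independent variables", and SAP 9.2 says "we will examine the main effect of aphasia type (adjusting for the other covariates) by tDCS group".

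SAP 8.7 attaches the abbreviation AQ to stroke severity. Protocol 2.2.2 describes it as "the Aphasia Quotient, which provides an overall measure of severity, in which lower scores denote more severe aphasia", meaning severity of aphasia.

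**The concern.** Under section 8.2 of the SAP (3.4.2 of the protocol), rejecting the null hypothesis ends further study of tDCS, and failing to reject keeps a Phase III trial open. That decision should rest on one model fixed in advance. Here there are two. Choosing between them once the data are unblinded would be an unplanned freedom in a decision that can stop development.

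There is also a technical point. When allocation is balanced on a prognostic factor and the analysis leaves that factor out, the usual standard error is too large, because it ignores the precision that the balancing gained. The test then declares futility less often than its nominal level implies, both when it should not and when it should. The estimate itself is not biased.

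Finally, neither document says how aphasia type is to be grouped in the model, so even the protocol's version is not fully specified.

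**Working it through.** **1. The lists side by side**

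| Factor | Protocol 3.2 allocation | Protocol 3.4.7 primary model | SAP 6 allocation | SAP 8.7 primary model | SAP 9.3 longitudinal model |
|---|---|---|---|---|---|
| Site | yes | yes | yes | yes | yes |
| Severity (AQ) | yes | yes | yes | yes | yes |
| Aphasia type | yes | yes | yes | **no** | yes |
| Age | no | no | yes | **no** | no |

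The protocol's model matches its own allocation factors. The SAP's model omits two of its four. The documents also disagree on whether age is an allocation factor.

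**2. The plan's own sample size**

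Inputs (SAP 8.3, protocol 3.4.3): margin 1.5, SD 2.6, one-sided alpha 0.10, power 85%.

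n per arm = 2 × [(z₀.₉₀ + z₀.₈₅) × 2.6 / 1.5]² = 2 × [(1.2816 + 1.0364) × 1.7333]² = 32.3, so 33.

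Exact t-test power is 85.2% at 33 per arm and 88.2% at 37. The inflation 33 / (1 − 0.05)² = 36.6 gives 37. The stated figures reproduce. They come from an unadjusted t-test, so they do not depend on the covariate list.

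**3. How the futility cut-off moves**

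Let R² be the share of outcome variance explained by the omitted factors beyond site and AQ. The documents give no value, so 0 to 0.30 is an assumption. Take 2.6 as the SD after site and AQ, with 37 per arm. In the normal approximation, futility is declared when the estimated difference is below

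c = 1.5 − 1.2816 × 2.6 × √(1 − R²) × √(2/37).

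With the factors omitted, c = 0.725. With them in the model, c = 0.765, 0.807 and 0.852 at R² 0.10, 0.20 and 0.30. An estimate between the two cut-offs is futile under one model and not under the other. The adjusted estimate also shifts with chance imbalance, so the rate of disagreement needs simulation.

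**4. SAP 8.7 model (site, AQ) against protocol 3.4.7 model (site, AQ, type)**

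Simulation of 74 patients, 10,000 replicates per setting. Assumed: 2 types (50/50) or 4 types (40/30/20/10%), and normal AQ and age. Allocation is sequential and never deterministic. Loose means a biased coin of 0.70, used only when a factor's imbalance statistic exceeds 1.04. Tight means minimisation with probability 0.90. Ranges span both rules and both type groupings. Percentage of trials with opposite futility verdicts:

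| True difference | R² 0 | R² 0.10 | R² 0.20 | R² 0.30 |
|---|---|---|---|---|
| 0 | 1–3 | 2–5 | 3–6 | 4–7 |
| 0.75 | 1–5 | 4–10 | 7–14 | 11–17 |
| 1.5 | 1–2 | 2–5 | 3–6 | 4–7 |

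A separately coded run (four types, minimisation probability 0.80, 3,000 replicates) gave 3.0, 5.3, 8.5 and 12.4% at a true difference of 0.75, inside these ranges. In that run the SAP model's false-futility rate was 7.9% at R² 0.20 and 6.6% at 0.30, while the protocol model stayed at about 10%.

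**5. SAP 8.7 model against a model with all four allocation factors of SAP 6 (site, AQ, type, age)**

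Neither document specifies this second model; it shows the cost of omitting everything the SAP balances on. There are four types, R² is split equally between type and age, and each setting has 20,000 replicates. False-futility rate with type and age omitted (nominal 10%; 9.7 to 9.9% when adjusted):

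| Allocation | R² 0.10 | R² 0.20 | R² 0.30 |
|---|---|---|---|
| Loose | 9.6% | 9.1% | 8.7% |
| Tight | 9.3% | 8.4% | 7.6% |
| Perfect-balance limit | 8.6% | 7.4% | 6.1% |

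The last row is 1 − Φ(t₀.₉₀,₇₂ / √(1 − R²)).

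Power to declare futility at a true difference of 0 is 88.6 to 90.8% with the factors omitted and 89.9 to 94.9% with them included, a gap of 1.2 to 5.1 points. At R² 0, including them costs 0.4 to 1.0 points from about 88%.

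**The case against.** The strongest reply is that the effect is small and cautious. At the two planning points (true difference 0 and 1.5) and R² 0.10, the models disagree in only 2 to 5% of trials, and 1 to 3% would disagree even if type explained nothing. The largest figures need both R² 0.30 and a true difference of 0.75, where the verdict is near a coin toss under either model: Φ((0.725 − 0.75) / 0.6045) = 48%, with 0.6045 = 2.6 × √(2/37). Aphasia type and AQ both come from the WAB-R, so type may add little beyond AQ. Omission introduces no bias, keeps false futility below 10% and leaves power above 85%. All of this stands, and it limits the weight of the point.

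Other parts stand in a narrower sense:

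- The absence of age from protocol 3.4.7 is consistent with protocol 3.2. The case for adjusting for age rests on SAP 6 alone.
- SAP 9.3 is exploratory and fitted within treatment group. It therefore shows only that the planners thought aphasia type worth modelling, not what the primary model must contain.
- The stroke-severity wording is probably a slip, since AQ identifies the variable.
- Protocol 3.2 refers to a separate Randomization Plan, which may define the type categories and settle the role of age. The allocation rules simulated here are stand-ins.

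None of this removes the contradiction. The two lists differ, no reason or order of precedence is given, and a small chance of opposite verdicts is still avoidable in a single go/no-go test.

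**Conclusion.** The concern holds. The conflict between protocol 3.4.7 and SAP 8.7 on aphasia type, and between protocol 3.2 and SAP 6 on age, is plain in the text and needs no assumption. Its practical size does depend on an assumed R². Over 0 to 0.30, the two documented models give opposite futility verdicts in 1 to 7% of trials at true differences of 0 or 1.5, and in 1 to 17% at 0.75. Omitting type and age makes the futility test conservative and costs a little power against the fully adjusted test, without bringing power below 85%. This should be corrected before the code is broken, but it does not undermine the design.

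**What to change.** Before unblinding, put one identical statement in SAP 8.7 and protocol 3.4.7, for example:

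*Linear model of the primary change score (average post minus average pre) on treatment, adjusted for every factor used in allocation: clinical site, aphasia type, baseline aphasia severity (WAB-R AQ), and age if it is used in allocation. Futility is declared if the one-sided 90% upper confidence bound for the adjusted A-tDCS minus S-tDCS difference is below 1.5. Aphasia type uses the categories of the randomisation program; categories with fewer than 5 patients on a blinded count are pooled by a rule fixed in advance.*

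The threshold of 5 is a suggestion; what matters is that the rule is fixed blind. Also reconcile protocol 3.2 with SAP 6 on whether age is an allocation factor, and change stroke severity to aphasia severity in SAP 8.7.

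Cost: no new data, since all four variables are already collected. With 2 to 4 type categories, the covariates use 4 to 6 of 72 degrees of freedom, of which site and AQ already take two. If the added factors are not prognostic, the loss is 0.4 to 1.0 points of power. SAP section 2 already plans an update before database lock and code break; the protocol sentence needs its own matching edit.

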1.2 Patient Exclusion Criteria

Patients with any of the following characteristics will not be eligible for entry into this study:

1. History of brain surgery
2. Seizures during the previous 12 months
3. Use of medications that lower the seizure threshold (e.g., Ritalin, Adderall, Bupropion, etc.)
4. Sensitive scalp (per patient report)
5. Able to overtly name more than an average of 140 out of 175 items during the pre-treatment picture naming test (Philadelphia Naming Test) during Visits 2 or 3
6. Unable to overtly name at least a total of 5 out of 160 items during the pre-treatment fMRI sessions during Visits 2 or 3

*The investigators in charge of this study are speech-language pathologists who have expertise in assessing, treating, consenting, and communicating with adults with speech-language impairment of many types and severities. It is important to note that aphasia is an impairment of speech-language, not intelligence, and that most often, in the absence of comorbid impairment(s), competence is not reduced but only masked by the speech-language impairment. The consent document is reviewed thoroughly, with verification questions asked frequently to ensure that the potential participant and his or her caregiver understand the scope of the research project. Only participants who clearly understand the research and are able to indicate consent to participate can be enrolled in this study. Caretakers, family, or friends must be present during consent approval, but they cannot consent for the participant. If written consent is not possible, they may act as witnesses for verbal consent. Crucially, because this population is not devoid of language and can make their wants, needs, and preferences known (either via impaired speech or via alternative communication modalities such as gestures, writing, etc.), participants who have the ability to consent also have the ability to inform the investigators that they wish to cease their participation if necessary.

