2. STUDY PROCEDURES

2.1 Study Procedures Overview

After informed consent is received, a neurological examination will be performed and multiple screening assessments will be conducted including a tDCS and MRI safety screening (see below). If the patient passes the initial screening portion, speech and language diagnostic testing will be conducted during the same visit (Visit 1). During the next two visits (Visits 2 and 3), patients will undergo baseline assessments of naming ability and connected speech, and structural and functional MRI examinations. The fourth visit will include collection of blood sample, electrode positioning and tDCS treatment administration. Patients will receive 15 sessions (Visits 4-18) of tDCS treatment administration. At the beginning of Visit 4, eligible patients will be randomized to receive either A-tDCS (1 mA) or S-tDCS (placebo) for 15 consecutive weekdays (20-min per each 45-min behavioral treatment session). A computerized anomia treatment will be coupled with the stimulation. The computerized treatment task will be 45-minutes in total length, so that it will commence at the same time as the tDCS administration and continue for another 25-minutes after the tDCS has ceased. To assess cardiovascular arousal, blood pressure and heart rate will be measured before and after each session. Additionally, discomfort ratings will be recorded following the end of each session using the *Wong-Baker FACES Pain Rating Scale* and a weekly neurological exam will be administered by a neurologist. Utilizing a computerized picture naming assessment (which combines the 175 items from the PNT and 80 treated items) of trained and untrained nouns, all patients will be assessed at 8 different time points throughout the experiment: twice at baseline (Visit 2 and 3), twice immediately following the fifteenth (and final) treatment session (Visit 19 and Visit 20), twice at 4 weeks follow-up (Visit 21 and Visit 22), and twice at 6 months follow-up (Visit 23 and Visit 24).

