8. PRIMARY ANALYSIS

8.1 Primary Outcome

The primary outcome will be the change in the number of correctly names items on the PNT (plus a portion [N=80] of the trained items) (where change from pre-treatment to immediate post-testing). To assess change in naming ability, the primary outcome in this study will be administered twice (and averaged to reduce variability) on two consecutive days immediately before treatment starts and twice after treatment is completed. The change will be computed as the difference in the number of correctly named items between the average of the two pre-treatment assessments to the average of the two post-treatment sessions. The PNT is a computer based assessment of naming in persons with aphasia and includes 175 pictures representing mid- and high-frequency nouns from a word frequency list compiled by Francis and Kucera (1982).

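### Adding the patient's own baseline naming score to the primary model would be an almost free gain in precision and conditional error; leaving it out does not make the planned analysis invalid

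*SAP*

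**What the plan says.** **Outcome.** SAP 8.1 takes the change "between the average of the two pre-treatment assessments to the average of the two post-treatment sessions". Protocol 3.4.1 uses the same difference of two-test means. The baseline score is therefore available for the analysis; Protocol 2.1 schedules the naming assessment "twice at baseline (Visit 2 and 3".

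**Covariates.** SAP 8.7: "The primary analysis will be adjusted for site and baseline stroke severity (AQ". Protocol 3.4.7: "The primary analysis will be adjusted for clinical site, aphasia type, and baseline aphasia severity (AQ". Neither list contains baseline naming.

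**Randomisation.** SAP 6 aims to "prevent serious imbalances in site, baseline age, aphasia type, and severity (as measured by the WAB-R". Protocol 3.2 describes allocation "controlling for clinical center, aphasia type, and severity (classified using the Western Aphasia Battery revised: WAB-R". Baseline naming is in neither.

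**Other uses of the baseline score.** Protocol 1.2 excludes a patient who is "Able to overtly name more than an average of 140 out of 175 items during the pre-treatment picture naming test". SAP 7 lists the PNT among the variables compared between arms at baseline, but attaches no adjustment to the result.

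**The concern.** A change score subtracts the baseline, but it removes the influence of the baseline completely only if the expected gain is the same at every starting level. Gain may vary with starting level, and measurement error in the baseline enters the change with a negative sign. In either case, a chance difference between arms in starting score carries over into the difference in change.

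AQ is only a partial stand-in. It comes from the WAB-R at Visit 1, a battery that also covers speech content, fluency, comprehension and repetition (Protocol 2.2.2). Two patients with the same AQ can start from different naming scores.

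The decision rests on 1.5 items. If the null hypothesis is rejected, tDCS is dropped from further study (Protocol 3.4.2, SAP 8.2). Two things are at stake: how far the result can be trusted given the imbalance that actually occurs, and the variance that an available covariate could remove.

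**Working it through.** **Inputs from the documents (SAP 4, 8.2 and 8.3; Protocol 3.4.2 and 3.4.3).** Margin 1.5 items; SD of change 2.6; one-sided alpha 0.10; power 85%; 33 per arm, inflated to 37; two-sample t-test.

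**Input that is assumed.** R², the share of variance in change that baseline naming explains beyond site and AQ. The documents give no figure, so a range of 0% to 30% is shown. The SD of 2.6 is used as if it were the SD left after site and AQ; the documents do not say that it is.

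**Step 1: reproduce the plan's sample size.** n = 2(1.282 + 1.036)² × 2.6² / 1.5² = 32.3, so 33 per arm. Noncentral-t power at 33 per arm is 85.2%. Inflation: 33 / 0.95² = 36.6, so 37. The plan's figures hold.

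**Step 2: shift from a chance imbalance.** With baseline SD s, the standard error of the baseline difference is s√(2/n), and the slope of change on baseline has size √R² × 2.6 / s. Their product is

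shift per standard error of imbalance = √R² × 2.6 × √(2/n).

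The baseline SD cancels. At n = 37, 2.6 × √(2/37) = 0.604.

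**Step 3: power with the covariate.** The residual SD is 2.6√(1 − R²). Power is noncentral t at 33 per arm, difference 1.5, one-sided 0.10.

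**Step 4: conditional error.** Suppose the true difference is exactly 1.5 and the arms differ at baseline by one standard error. By normal approximation, the chance that the unadjusted test declares futility is Φ[(−1.282 ± √R²) / √(1 − R²)], the sign depending on which arm is favoured.

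| Assumed R² | Shift, 37 per arm (items) | Share of 1.5 margin | Adjusted residual SD | Power, 33 per arm | False-futility chance given a 1-SE imbalance, unadjusted |
|---|---|---|---|---|---|
| 0% | 0 | 0% | 2.60 | 85% | 10% |
| 1% | 0.06 | 4% | 2.59 | 85.5% | 8.2% or 11.8% |
| 10% | 0.19 | 13% | 2.47 | 88% | 4.6% or 15.4% |
| 30% | 0.33 | 22% | 2.18 | 93% | 1.4% or 19.0% |

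For scale, at 37 per arm futility is declared when the observed difference falls below about 0.72 items.

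**Step 5: how much could measurement error alone explain?** Assign all the variance of change to test noise. Each two-test mean then has error variance 2.6² / 2 = 3.38, and the slope of change on baseline is −3.38 / s². At an assumed baseline SD of 45, one standard error of imbalance is 45 × √(2/37) = 10.5 items, and the shift is 3.38 / 45² × 10.5 = 0.017, or about 0.02 items. The implied R² is (3.38 / (2.6 × 45))², about 0.1%. At an assumed SD of 10 the shift is still only about 0.08 items. A shift of 0.19 or more would need gain itself to depend on starting level after AQ has been allowed for.

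**The case against.** The strongest objection is that nothing the plan promises fails. The outcome already subtracts each patient's baseline, and randomisation makes the difference in change unbiased. The 10% and 15% error rates average over chance baseline imbalance, because any baseline-related variance is already inside the SD of 2.6. The trial reaches its 85% power without the covariate. All of this stands.

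A reader might infer that the omission adds a risk of false futility, or of wrongly moving to Phase III, beyond the planned rates. The documents do not support that. The last column of the table averages back to 10% over all possible imbalances; it describes the error given the sample obtained, not an excess.

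The proposed mechanisms also look weak on the plan's own figures. A ceiling on the PNT is unlikely to bind. The exclusion at an average above 140 of 175 leaves at least 35 PNT items of headroom against a planned gain of 4 to 5.5, and (35 − 5.5) / 2.6 is more than 11 SDs. That argument covers the 175 PNT items only, since the entry rule does not cap the 80 trained items. Measurement error contributes little (Step 5). Part of any severity-related gain is already taken up by AQ as a covariate and by balancing on severity and aphasia type.

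Finally, the size restates the assumption: the shift divided by the standard error of the arm difference is √R², so choosing R² chooses the answer. That is correct, and it is why the range starts at zero. It does not argue against a covariate that costs almost nothing when R² is zero.

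A reader might also infer from the entry rules that patients span nearly the whole naming range, so that imbalance must be large. This is not established. Protocol 1.1 also requires 65% on a naming screen, and Protocol 2.2.1 leaves unclear how that task relates to overt naming. The calculation does not need the point, because the baseline SD cancels in Step 2.

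**Conclusion.** The omission is real and is found in both documents. The planned analysis remains unbiased with valid overall error rates, and its sample size reproduces. What is lost is precision, and control of error conditional on the baseline imbalance that occurs.

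The size cannot be fixed from the documents. It is negligible if baseline naming explains 1% or less of the change beyond site and AQ, and useful at 10% or more: a shift of 0.19 items or more per standard error of imbalance, and power of 88% or more. These figures assume a linear relation that is the same in both arms, and an SD of 2.6 after site and AQ. The change is worth making because it costs so little, not because the current plan is in error.

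**What to change.** In Protocol 3.4.7 and SAP 8.7:

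- Add the mean of the two baseline naming scores (Visits 2 and 3) as a continuous covariate in the primary model, on the same item set as the outcome. The item set needs stating, because SAP 8.1 includes the 80 trained items in the outcome while the opening definition in Protocol 3.4.1 refers to the PNT.
- State that the covariate-adjusted arm difference is the quantity tested against 1.5.
- Include the same variable in the multiple-imputation model (Protocol 3.4.5, SAP 8.5), whose contents are not listed.

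The two covariate lists already differ on aphasia type and need reconciling, so one edit can do both.

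The cost is one degree of freedom and wording changes before unblinding. If baseline naming explains nothing, power at 33 per arm remains 85.2%. No new data are needed, and SAP 2 already provides for an update before database lock and code break.
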